Participants will be fitted with a BioNomadix RSP respiratory transducer belt and amplifier. Respiration rate will be recorded with MP160 and digitized using AcqKnowledge at rest and throughout the entire session.

We will test the analgesic effects of light slow brushing, deep pressure, and neutral touch (tapping) on induced pain using a modified affective-CPM paradigm. In this session, we will test the effect of non-painful touch stimuli on the conditioned pain stimulus, as has been conducted by [6, 7]. Both segmental (same dermatome) and nonsegmental (different dermatome) effects will be tested in order to determine whether pain inhibition is a bottom-up neural effect or an indirect affective effect.

After identifying limb locations identified as most comfortable by patients, we will perform calibration and will administer six affective-CPM blocks in an order counterbalanced across subjects: brushing, pressure, and

tapping, repeated with testing within a segment (same dermatome) and outside a segment (different dermatome).

Calibration (psychophysical testing): Session 2 calibration will be confirmed by testing the temperature rated as a 6 in Session 1 and adjusting as necessary.

Each affective-CPM block will include: phasic heat pain (baseline), heat pain with concurrent touch stimulus (test), and then test phasic heat perception once again (post-test), as follows:

Baseline: Heat will be administered using a thermode for 30s. Pain intensity ratings for the heat will be collected every 10s for a total of 3 ratings.

Test: 0-30s: rate pleasantness and intensity of the touch stimulus (brushing, pressure, or tapping). 30-60s: administer heat pain using a thermode concurrently; pain intensity rating of heat pain given every 10sec for a total of 3 ratings

Post-test: Repeat of baseline.

Between blocks the participant will rest for approximately 10-15min until sensation has dissipated to avoid habituation to test stimuli.

Session 2 will occur at the ACTRI and will take approximately 1-2 hours to complete.

Session 3: MRI Session for healthy controls (optional, offered until $N = 20$ controls have completed MRI)

A urine pregnancy (if applicable) test will be performed.

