We expect that FM patients will show reduced pleasantness of C-LTMR-optimal touch compared to healthy individuals as found in FM patients in [3] and LBP patients in [8]. We hypothesize that current depression and trauma history will be significant predictors of blunted C-LTMR touch pleasantness. Based on an effect size F^2 of 0.15, three predictors, alpha of 0.05, and power 0.8, this study will require $N = 77$ participants. We will round up to $N = 80$ and include $N = 40$ FM patients and $N = 40$ healthy controls. Based on effect sizes observed in [3] and [8], this sample size will also be sufficient for the comparisons of pleasant touch.

Furthermore, we expect that FM patients will show reduced analgesic benefit of pleasant touch compared to healthy controls, due to reduced touch pleasantness ratings and our theorized relationship between touch pleasantness perception and analgesia, and due to reduced endogenous pain modulation evidenced in the CPM paradigm. We expect reduced analgesic effects of touch pleasantness in FM due to altered pleasant touch perception in FM (and LBP) [3, 8]. The studies showing analgesic effects of affective touch showed effect sizes of approximately $d = 0.6$ [6] and $d > 2$ (for the large compression area) [7], respectively. We would need 24 participants to demonstrate the smaller effect size in each group (alpha of 0.05, power of 0.8). No previous study has examined how pleasant touch modulates pain in chronic pain compared to healthy adults. To observe a difference in affective pain modulation between patients and healthy controls, based on the average large effect size of 0.78 seen across studies in [27] for CPM, this study would require 27 participants in each group, so the 40 participants calculated for each group will be sufficient. The MRI portion of the study will be a pilot study ($N = 20$), intended to provide preliminary data for future grant applications.

Data Analyses and Interpretation

Scores on the depression and trauma history questionnaires will be used as linear regressors to predict ratings of gentle brushing pleasantness.

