Cold- and Affective-CPM: We will average the pain ratings from each stimulus period and compare the percent change of baseline to post-test ratings as our primary outcome measure. We will use ANOVA to compare differences between baseline and post-test between touch types, within or between dermatomes/segments, and between patients and healthy volunteers. A linear regression will be used to determine whether baseline touch pleasantness ratings significantly predict the CPM effect for each type of touch.

ASL/fMRI: Periods of baseline pain will be contrasted with periods of touch concurrent to pain (test) and following pain (post-test) in brain areas involved in pain processing. Connectivity analyses will be performed to identify the source of significantly reduced pain response in any of these areas during affective touch.

Inclusion of Women and Minorities:

Participants will include all genders and races. Based on the latest San Diego-based demographic consensus, we plan to recruit 60% White, 16% Asian, 7% Black, .5% Native American, .5% Pacific Islander, 12% Other race, 5% two or more races. We expect that 29% of our participants will be Hispanic or Latino. If necessary to obtain minority representation, under-represented racial groups will be targeted specifically for recruitment.

Rates of FM are higher in females than in males (9:1 ratio) [28], so an approximately 9:1 ratio is expected in the current study. All races and ethnicities will be invited to enroll. Expected demographics are based on the latest San Diego-area demographic census. If needed, to increase minority representation, recruitment efforts will include targeted advertising (e.g., flyers, postings, community outreach presentations) in communities with high minority populations and through community-based talks given by the PI and staff.

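### Block position is left out of the Session 2 ANOVA, so any drift in the percent-change score across the six blocks stays in the error term; adding it is a cheap gain in precision

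*Combined protocol and SAP*

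**What the plan says.** Section 9, Session 2: Affective-CPM Paradigm, crosses three touch types (brushing, pressure, tapping) with two locations (same or different dermatome). The investigators "will administer six affective-CPM blocks in an order counterbalanced across subjects". No sequence scheme is named, and nothing is said about balance of order within FM or within controls. Section 10 matches the two groups on age and sex only.

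Each block has its own heat baseline, a test period with concurrent touch, and a post-test. The same section provides a safeguard: "Between blocks the participant will rest for approximately 10-15min until sensation has dissipated to avoid habituation to test stimuli".

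Under Data Analyses and Interpretation, ratings are averaged within each stimulus period and the investigators will "compare the percent change of baseline to post-test ratings as our primary outcome measure". The model follows: "We will use ANOVA to compare differences between baseline and post-test between touch types, within or between dermatomes/segments, and between patients and healthy volunteers". No block position, order or sequence term appears there or elsewhere. The planned sample will "include $N = 40$ FM patients and $N = 40$ healthy controls".

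**The concern.** Each participant receives 6 blocks x 3 heat periods = 18 thirty-second painful heat exposures in Session 2, at a temperature confirmed once at the start. The stated purpose of the rests shows that the investigators see habituation as a risk. If the percent-change score still moves with position, the design has controlled a source of variation that the analysis then ignores. Counterbalancing spreads drift over the conditions. It does not take drift out of the residual unless position is in the model.

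The contrasts exposed are those between blocks within a person: between touch types, between segments, and either of these by group. They bear on the prediction in section 7 that pleasant touch relieves pain more than neutral touch, and on whether that advantage differs in FM.

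**Working it through.** **The plan's own figures.** Under Sample Size Determination & Power, all three sample sizes reproduce, and none depends on block order:
- two-sample two-sided t, d = 0.78, alpha 0.05, power 0.8: 27 per group;
- paired two-sided t, d = 0.6: 24;
- regression with f² = 0.15 and three predictors: N = 77.

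**Inputs.** From the documents: six blocks, 40 per group, alpha 0.05, power 0.8. Assumed, because the documents give no SD and no drift: a linear drift of total size D over the six positions, in units of the within-person SD of the block change score, shown for D = 0.25 to 1.5.

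**Variance cost with random orders.** The drift per block is D/5. The within-person variance of positions 1 to 6 (divisor 5) is 17.5/5 = 3.5. With position omitted:

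variance factor = 1 + 3.5 x (D/5)²

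- D = 0.25: 1 + 3.5 x 0.0025 = 1.009
- D = 0.5: 1 + 3.5 x 0.01 = 1.035
- D = 1.0: 1 + 3.5 x 0.04 = 1.14
- D = 1.5: 1 + 3.5 x 0.09 = 1.315

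**Power.** The contrast is brushing minus tapping (mean of two blocks each), FM minus controls. With 40 per group and no drift, its standard error is √(2/40) = 0.224 SD, and 80% power corresponds to d = 0.63. Dividing that effect by the square root of the variance factor gives power of 79.7%, 78.6%, 74.7% and 68.6% for the four values of D.

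**Calibration.** Type I error (no true effect) for the same contrast, 3,000 simulated trials per cell, linear position covariate where adjusted:

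| Total drift D | Random orders, no position | Balanced within group, no position | Position in the model (both schemes) |
|---|---|---|---|
| 0.5 | 4.8% | 3.9% | 4.7-5.2% |
| 1.0 | 5.5% | 2.7% | 4.8-5.2% |
| 1.5 | 4.6% | 1.4% | 5.4-5.6% |

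The third column falls below 5% because balancing within group keeps drift out of the estimate while it stays in the residual, so the standard error is too large. With position modelled, simulated power for d = 0.63 was 78-81% at every D from 0 to 1.5.

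**Does order shift the FM-control touch contrast?** With independent random orders, the group difference in mean contrast position averages zero, with SD √(3.5 x 2/40) = 0.42 positions (simulated 0.41). At D = 1 that is 0.41 x 0.2 = 0.08 SD, against a standard error of 0.22. It is chance variation that the standard error already reflects. Opposite drifts in the two groups (+0.2 and -0.2 SD per block, then +0.3 and -0.3), checked on the contrast of four pleasant minus two tapping blocks, gave type I error of 5.0% and 5.2% with mean bias near zero.

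**What is not exposed.** Every participant who completes all six blocks occupies each position once (sum 21), so the FM-control difference averaged over the six blocks does not depend on order. For the four pleasant-touch blocks alone, write p and t for the mean positions of pleasant and tapping blocks. Then 4p + 2t = 21, so p - t = 3p - 10.5. The group gap in p is therefore one third of the gap in p - t: SD 0.12 positions against 0.36.

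**The case against.** The best defence is that the outcome is already protected. Each block has its own baseline, the score is change from that baseline, and 10-15 minutes of rest separate the blocks. Drift in raw pain is then largely removed. Suppose, with assumed figures, that baseline falls from 6 to 5 over the session while touch always takes off 1.2 points. Percent change moves from -20% to -24%. If its SD is 20-30 points, that is 4/30 to 4/20 = 0.13-0.2 SD in total, and the variance factor is at most 1 + 3.5 x (0.2/5)² = 1.006. Drift of 1.0-1.5 SD in the change score has no support in the documents.

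Most of this stands, and it is why the point is minor. It does not remove the point. Percent change has the drifting baseline in its denominator, and modulation that fades or grows with repetition is untouched by a block-specific baseline.

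A second defence is that the wording on counterbalancing is ordinary and does not exclude balance within each group. That is correct: the text is silent. But if orders are balanced within group, omitting position makes the test conservative, so the model change is useful under either reading.

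Third, the plan needs 27 per group for the FM-control difference and enrols 40. That margin is real, but it was calculated for the overall group difference, not for a group-by-touch contrast.

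**Conclusion.** The omission is confirmed; its cost is modest and depends on an unknown drift. Up to 0.5 SD of total drift in the change score, it costs at most 3.5% in error variance and about one power point. At 1.0 SD it costs 14% and about five points; at 1.5 SD, 31.5% and about eleven points. These figures assume linear drift, complete blocks and equal residual variance in all blocks. The larger drifts are probably too high given the block baselines.

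A reader might infer that drift leaks into the FM-control comparison and produces a spurious group-by-touch effect, especially if FM patients sensitise while controls habituate. The documents do not support that. They do not say that order is balanced only in the pooled sample. With random orders, type I error stays near 5% and bias near zero, even with opposite drifts. Inflation appeared only in a constructed worst case: one six-row list shared by all subjects with strictly alternating FM and control enrolment, where type I error reached 6.4%, 8.5% and 10.9% at D = 0.5, 1.0 and 1.5. No section describes such an allocation.

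This is therefore a point about precision and calibration: a cheap improvement, minor in weight.

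**What to change.** In section 9, Data Analyses and Interpretation, specify a repeated-measures or mixed model with touch type, segment, group and block position (1 to 6) as a within-person factor. Add position-by-group as a sensitivity analysis.

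In section 9, Session 2, name the order scheme and run it separately within FM and within controls, for example as a six-sequence Williams square. Since 40 = 6 x 6 + 4, four sequences would be used seven times and two six times in each group (4 x 7 + 2 x 6 = 40), so balance is near rather than exact. The position term deals with the remainder.

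The cost is two sequence lists, a sentence of analysis text, and 5 of (80 - 2) x 5 = 390 within-person degrees of freedom, or 10 with position-by-group. No new data and no change in sample size are needed.

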
The proposed research is the subject of a pending R00 award and will determine whether light and deep pressure touch have comparable analgesic effects, and whether these effects differ in individuals with chronic pain conditions. It will also determine which factors predict the blunted affective touch perception observed in patients with chronic pain. The central hypothesis is that both light and deep pressure touch exert analgesic benefits, and that these analgesic effects will correlate with the pleasantness of touch. Further, we predict that the analgesic effects of pleasant touch will be reduced in patients with chronic pain, who experience reduced touch pleasantness. This research will advance our understanding of the mechanisms of massage therapy and its effect on those who suffer from chronic pain.

Aim 1 (R00): Determine why individuals with chronic pain show reduced C-LTMR-related touch pleasantness.

Hypotheses: I hypothesize that blunted pleasantness of C-LTMR and deep pressure touch in individuals with chronic pain will be predicted by psychological factors including depression and trauma history (due to the impact of these factors on the μ -opioid system, e.g. [9]).

Aim 2 (R00): Determine whether the analgesic effects of light and deep pressure touch are reduced in individuals with chronic pain, and whether analgesia correlates with pleasantness perception.

Hypotheses: I hypothesize that concurrent or recent administration of light or deep pressure pleasant touch will reduce the perceived pain of a phasic heat stimulus, and that this effect will be reduced in chronic pain patients. Further, I predict that the analgesic effect of affective touch will be correlated with the perceived pleasantness of the touch.

Sub-aim 2b: Determine whether CPM effects of pleasant touch are related to CPM effects of pain.

Hypotheses: I hypothesize that the CPM efficiency for painful and pleasant touch will not be correlated across participants, suggesting divergent mechanisms.

Sub-aim 2c: Determine whether analgesic effects of light stroking or deep pressure are mediated by reductions in respiration rate.

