Hypotheses: I hypothesize that changes in respiration rate will predict the analgesic (CPM) effect for pleasant touch, suggesting central modulation of pain by pleasant affect-induced changes in respiration. In addition, I predict that there will be interindividual differences in respiration at baseline that correlate with pleasantness perception and respiratory-related pain modulations.

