We will then familiarize participants with our touch tasks and collect baseline ratings. A brief training will be conducted to introduce sensations and rating scales. We will then collect several rounds of ratings of approximately 1 min each of light gentle brushing (using a soft paint brush), deep pressure (using a lymphedema compression sleeve inflated to <100mmHg or a commercially available massager), a neutral touch (tapping), and heat pain using a Medoc or Thermal QST thermode. Testing will occur on the limbs in areas identified as most comfortable by patients. Participants will be asked to rate their mood at various timepoints throughout the study.

Finally, we will conduct a classic CPM paradigm with a cold water bath where participants immerse their forearm into a 12°C refrigerated circulating water bath (e.g. NESLAB Digital One RTE 7, Thermo Scientific, Newington, NH, USA) for 60 seconds. The CPM paradigm is used to test the analgesic effects of a concurrent or recent test pain stimulus on a conditioned pain stimulus. The effects of the cold-CPM paradigm will be contrasted with a modified affective-CPM paradigm in Session 2. The cold-CPM block will include: phasic heat pain (baseline), heat pain while concurrently placing hand in the cold water bath (test), and then test phasic heat perception once again (post-test), as follows:

Calibration (psychophysical testing): determine level of heat to administer that results in a verbal pain rating of 6 out of 10 (0 = no pain; 10 = intolerable pain). An ascending series of 10s-duration heat stimuli between 39 and 50C will be administered until a stimulus is rated as a 6 out of 10. If a 6 is surpassed, stimuli will be decreased in .5C increments until the rating of 6 is achieved. Ratings will be confirmed by administering a 30s stimulus and adjusted if necessary.

Baseline: Heat will be administered using a thermode for 30s. Pain intensity ratings for the heat will be collected every 10s for a total of 3 ratings.

Test: 0-30s: rate unpleasantness and intensity of the cold water stimulus. 30-60s: administer heat pain using a thermode concurrently; pain intensity rating of heat pain given every 10sec for a total of 3 ratings

Post-test: Repeat of baseline.

Session 1 will occur at the ACTRI and will take approximately 1 hour to complete.

Session 2: Affective-CPM Paradigm

A urine pregnancy (if applicable) and opiate test will be performed.

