We will test the analgesic effects of affective touch on induced pain using BOLD fMRI or arterial spin labelling (ASL) in 20 healthy participants using the same test paradigm conducted in Session 2. Neural responses will be compared during the periods of thermal heat pain with versus without concurrent or recent touch.

The MRI session will occur at the UCSD Center for Functional MRI (CfMRI) and will take approximately 2-3 hours to complete.

Timeline

Sessions may be completed on the same day or on different days according to the participant and experimenters' availability. After providing written consent (active enrollment), subjects will have 4 months to complete Sessions 1 and 2 or they may be dropped from the study if the study team cannot accommodate an extension. Any spacing of sessions is acceptable. A single reschedule may be allowed for participants who fail a drug screen due to recent consumption of poppy seeds (if not previously aware) or if there are any technical issues in the session. MRI sessions will be offered to healthy volunteers until 20 have completed the MRI session. These sessions will be filled on a first-come-first-served basis.

Outcome Measure(s)

Visual Analog Scale (VAS): Pain ratings and touch pleasant/unpleasantness ratings will be assessed in response to each sensory stimulus at baseline (Session 1) and during the baseline and post-tests in the cold- and affective-CPM blocks. On each scale the minimum rating will be designated as "no pain/unpleasantness/pleasantness" and the maximum will be labeled as "most intense imaginable" or "most unpleasant/pleasant imaginable."

Cerebral blood flow (average blood perfusion; mL blood/100 grams tissue/minute): changes in cerebral blood flow (CBF) will be assessed during arterial spin labeling MRI to compare processing of pain before, during, and after affective or control touch conditions. The MRI portion of the study is a pilot study.

Sample Size Determination & Power

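### Heat ratings taken during touch or cold water are outside the primary measure and the ANOVA, so the concurrent part of Aim 2 has no stated behavioural contrast

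*Combined protocol and SAP*

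**What the plan says.** All references are to the combined protocol and SAP.

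- **Section 6, Aim 2.** The hypothesis is that "concurrent or recent administration of light or deep pressure pleasant touch will reduce the perceived pain of a phasic heat stimulus", and that the effect will be smaller in patients with chronic pain.
- **Section 9, Session 1 and Session 2.** Each cold or touch block has a baseline, a test and a post-test phase. Three heat-pain ratings are taken in each phase. In the test phase they fall at 30-60 s, with the cold water or touch still applied. The conditioning stimulus itself is rated at 0-30 s of that phase.
- **Section 9, Outcome Measure(s).** Besides the Session 1 baseline ratings, pain and touch ratings are listed only "during the baseline and post-tests in the cold- and affective-CPM blocks".
- **Section 9, Data Analyses and Interpretation.** Ratings are averaged within each stimulus period. The plan will then "compare the percent change of baseline to post-test ratings as our primary outcome measure". It continues: "We will use ANOVA to compare differences between baseline and post-test between touch types", and also by segment and by group. A regression asks "whether baseline touch pleasantness ratings significantly predict the CPM effect for each type of touch".
- **Section 6, sub-aims 2b and 2c.** The predictions are that "the CPM efficiency for painful and pleasant touch will not be correlated across participants" and that "changes in respiration rate will predict the analgesic (CPM) effect for pleasant touch". Neither names a phase.
- **Section 9, ASL/fMRI.** Baseline pain is contrasted with both the test and the post-test periods, as neural responses, in a pilot of 20 healthy participants.

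**The concern.** The design measures two things: how painful the heat is while touch is applied, and how painful it is afterwards. The aim names both, but the behavioural analysis uses only the second.

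If touch relieves pain mainly while it is applied and the relief fades quickly, the stated primary measure and ANOVA would show little or nothing, although the relevant ratings had been collected. The same holds for a difference between fibromyalgia patients and controls that exists only during touch. An investigator who then looked at the test-phase ratings would be making an unplanned comparison, and the result could only be reported as post hoc.

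A second, smaller problem is that the CPM effect is not defined by phase. Session 1 introduces the paradigm in words that fit either phase: "The CPM paradigm is used to test the analgesic effects of a concurrent or recent test pain stimulus".

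**Working it through.** **The plan's own figures.** Section 9 gives three sample sizes, and all reproduce at 80% power and alpha 0.05 (two-sided for the t-tests):

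- multiple regression with f² = 0.15 and three predictors: 77 in total (stated 77);
- paired t-test with d = 0.6: 24 per group (stated 24);
- two-sample t-test with d = 0.78: 27 per group (stated 27).

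The point concerns which contrast is defined. It depends on none of these figures and changes none of them.

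**Which analysis uses which phase.**

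| Place in the document | Baseline | Test (concurrent) | Post-test |
|---|---|---|---|
| Aim 2 hypothesis | reference | yes | yes |
| Heat ratings collected, Sessions 1 and 2 | 3 | 3 | 3 |
| Outcome list | yes | no | yes |
| Primary percent change | yes | no | yes |
| ANOVA | yes | no | yes |
| Imaging contrast (neural, 20 healthy) | yes | yes | yes |

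The outcome list, the primary measure and the ANOVA all name the same two phases, so this is not a single slip of wording. The imaging row shows that the authors can specify a test-phase contrast. That contrast has no patient group and is not a comparison of perceived pain.

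**Ratings left out.** There are six touch blocks (three touch types, each within and outside the segment) and one cold block.

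- Heat ratings per block: 3 phases × 3 = 9.
- Per participant: 7 × 9 = 63, of which 54 are in touch blocks and 9 in the cold block.
- Test phase: 7 × 3 = 21, of which 18 are in touch blocks and 3 in the cold block.
- Over 80 participants, if all complete every block: 80 × 63 = 5,040 ratings, of which 80 × 21 = 1,680 are outside the primary measure and the ANOVA.

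**Cost of choosing the phase after seeing the data.** Take two true null hypotheses, each tested at two-sided 5%, with the better result reported. If the two tests are perfectly correlated, the error rate stays at 5%. If they are independent, it is 1 − 0.95² = 0.0975. Under bivariate normality, other correlations fall between these, so the range is 5% to 9.75%. The documents do not give the correlation.

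**Timing of the touch and cold-water ratings.** The outcome list places in-block pleasantness and unpleasantness ratings in the baseline and post-test phases. According to the session descriptions those phases contain heat only, and the conditioning stimulus is rated at 0-30 s of the test phase. The two descriptions do not agree.

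**The case against.** Several points on the other side are sound.

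- The Aim 2 hypothesis is worded as one timing or the other. Comparing baseline with post-test tests one of the two, and the primary measure is valid for it. A reader might infer that the primary is wrong or should be replaced; the documents do not support that.
- A reader might infer that the test-phase ratings are simply discarded. The plan averages ratings from every stimulus period, which includes the test period. That shows an intention to process them, but no behavioural contrast is attached to the average.
- A reader might infer that the outcome of the pleasantness regression cannot be determined. That goes too far. The CPM effect appears in the same paragraph as the primary measure, two sentences later, and most naturally means the baseline to post-test percent change. The term still needs a definition.
- For sub-aims 2b and 2c, the Data Analyses section states no analysis at all. The unnamed phase is only part of that gap, and counting alternative versions of an unstated analysis would have no basis.
- Nothing in the documents suggests that a phase will be chosen for its result. The primary is fixed, so a switch there would be visible. The inflation is conditional and concerns only added or undefined analyses. It does not apply to sub-aim 2b, which predicts no correlation: a favourable choice there would be a non-significant result, which is not a false positive.

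None of this supplies a behavioural contrast for the concurrent phase.

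**Conclusion.** The point holds and should be fixed. The after-effect of touch is tested by a valid primary measure; the effect during touch, and its comparison between fibromyalgia and control participants, has no stated behavioural test. One third of the block heat ratings (21 of 63 per participant) are outside the primary measure and the ANOVA. That count follows from the block design, and the study-wide total assumes complete data from all 80 participants.

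The undefined CPM effect and the mismatch in rating times are secondary. The error range of 5% to 9.75% describes what post hoc phase choice would do under bivariate normality; it is not a claim that such a choice is planned. No sample size is affected. The documents do not say which phase the cited effect sizes of 0.6 and 0.78 refer to, so their match to the primary measure cannot be checked.

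**What to change.** 1. Keep the baseline to post-test percent change and its ANOVA as primary, unchanged.
2. Add a pre-specified secondary ANOVA on baseline-to-test percent change by touch type, segment and group. For the cold block, which has neither touch type nor segment, add the overall change and the group comparison. Place these after the primary in the testing order.
3. Report concurrent effects and after-effects separately. The concurrent effect may include distraction, for which tapping is the comparator.
4. Define the CPM effect as 100 × (mean of the 3 ratings in the named phase − mean of the 3 baseline ratings) / mean of the 3 baseline ratings. Name the phase for the pleasantness regression, for sub-aim 2b (both cold and touch) and for sub-aim 2c, and state an analysis for the two sub-aims.
5. Amend Outcome Measure(s) to list the test-phase heat ratings and to place both the touch and the cold-water ratings at 0-30 s of the test phase, as in the session descriptions.

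The cost is wording only, with no new data, visits or participants. The statistical price is up to 10 more secondary tests. For the touch blocks there are 3 main effects + 3 two-way terms + 1 three-way term = 7, plus the overall change = 8. The cold block adds 2.
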